### **10.3.3 Metrics**

Of the patients who receive a V-CST referral from their HCS, the percentage who enroll in V-CST will be the primary enrollment metric. This metric will be calculated for each site to assess any site-level differences, and for sub-populations of patients to assess any individual level differences including by race, gender, and ethnicity.

Attendance at V-CST groups will be tracked to assess individual adherence at the individual level. The individual level metric will be the percentage of the 14 V-CST sessions that each intervention group member attends. The distribution of this metric across sub-populations of patients also will be calculated to assess differences by race, gender, and ethnicity.

Attrition from V-CST, indicated by the percentage of enrolled participants who stop attending V-CST between S1 and S14 also will be calculated.

The number of AEs will be assessed at the individual level, and the distribution of the number of AEs that each participant experiences will be calculated. Additionally, this metric, the number of AEs experienced by each participant, will be summed across all V-CST participants and among sub-populations of patients, including by race, gender, and ethnicity.

The completeness of outcomes data will be measured at the individual participant level to assess the quality of outcomes data with each instrument (i.e., MMSE, MoCA, SLUMS). The percentage of items with missing data will be calculated per V-CST participant as the primary quality control metric to be used for outcome measures. This metric also will be calculated for sub-populations of patients to determine individual level differences including by race, gender, and ethnicity.

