### **6.2.3 Treatment Sessions**

Over the course of 14 treatment sessions in 7 V-CST groups, five process measures will be collected by the V-CST facilitators at each session:

- Patient attendance (percentage of 14 sessions attended)
- Protocol fidelity: CST protocol followed per Therapy Administration Form
- Attrition: Patient dropping out of V-CST group and stopping attendance
- Weekly Monitoring CST Participant Progress reports
- Adverse Events

V-CST will end after the 14 sessions (plus orientation and closeout sessions) and participants continue with their standard of care treatment at their HCS.

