## **7.2 Methods and Timing for Assessing, Recording, and Analyzing Safety Parameters**

There are no documented harmful side effects from receiving a referral for or participating in CST (Orrell et al., 2017; Spector et al., 2003). Although the minimal risk of CST has been established and our online delivery further reduces risk for harm, care will be taken to assess, record, and analyze safety parameters.

V-CST facilitators will monitor participants for harm at all times during therapy delivery. Should a safety event occur, the event will be addressed by the PI upon receiving the adverse event report and reported to the Safety Officer.

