## **7.3 Adverse Events and Serious Adverse Events**

Definitions for adverse events (AEs), serious adverse events (SAEs), and Unanticipated Problems (UP) to be used for this trial are provided below:

**Adverse Event (AE):** Any unfavorable medical occurrence in a clinical research study participant, including any abnormal sign (e.g., abnormal physical exam or laboratory finding), symptom, or disease, temporally associated with the participants’ involvement in the research, whether or not considered related to participation in the research.

**Serious Adverse Event (SAE):** Any adverse event that:

- Results in death,
- Is life threatening, or places the participant at immediate risk of death from the event as it occurred,
- Requires or prolongs hospitalization,
- Causes persistent or significant disability or incapacity,
- Results in congenital anomalies or birth defects,
- Is another condition which investigators judge to represent significant hazards.

**Unanticipated Problems (UP):** Any incident, experience, or outcome that meets all of the following criteria: unexpected, in terms of nature, severity, or frequency, given (a) the research procedures that are described in the protocol-related documents, such as the IRB-approved research protocol and informed consent document; and (b) the characteristics of the study population; related or possibly related to participation in the research; suggests that the research places participants or others at a greater risk of harm (including physical, psychological, economic, or social harm) than was previously known or recognized.

As stated above, one possible AE for this study is increased stress. For example, it is possible that the group discussion that takes place will increase participant stress. Increased stress is a possible mild AE of CST. This study has no other AEs.

No SAEs are expected. No AEs or SAEs of CST have been reported in over 15 years of studies. CST involves group discussions, and in this trial, CST will be delivered online to prevent infectious disease transmission.

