Although hospitalizations and death or not uncommon in this population in general, they are unlikely to be related to the study. In the event of hospitalizations or death of V-CST participants identified by the V-CST facilitators, the lead facilitator will report this information to the referring physician per standard of care practice. In the event of hospitalizations or death of any study participant (intervention or control group) identified by the referral site, the referral site will report this information to the study coordinating site (UMass).

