### **9.3 Interim Analyses and Stopping Rules**

Although no AEs are anticipated, the possibility of AEs will be monitored at every V-CST session, and specifications are established for discontinuing participant involvement in V-CST should they arise, as described above. The primary potential risk of V-CST is an increase in stress among participants, such as if participants are argumentative or confrontational with each other.

During V-CST sessions, the facilitators will observe participants for expressions or signs of increased stress or argumentative or confrontational behavior, such as yelling, cursing, or arguing with other participants. V-CST facilitators will immediately intervene when such signs are observed, such as to redirect the discussion to another topic. Participant involvement in V-CST will be discontinued temporarily or for the remainder of the treatment pending the frequency of these extreme stress instances and the responsiveness of the participant to redirection. Participant involvement in V-CST will be temporarily discontinued (for the remainder of the session) when more than one instance of such heightened stress is observed during a single V-CST session. Additionally, participant involvement in V-CST will be discontinued altogether when instances of such heightened stress are observed in more than two separate V-CST sessions.

In any V-CST group where more than one participant's involvement in V-CST is discontinued altogether due to multiple AEs, findings will be presented to the study statistician to review the events by group to determine whether there are statistical as well as clinical concerns. The statistician will report his findings to the project Safety Officer. The findings will be used to determine what steps will be taken.

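### Section 10.3.3 sums session-observed adverse events by subgroup with no denominator, so the sums mix risk with subgroup size and attendance

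*Combined protocol and SAP*

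**What the plan says.** Section 10.3.3 (Metrics) defines two AE summaries. First, "the distribution of the number of AEs that each participant experiences will be calculated". Second, "the number of AEs experienced by each participant, will be summed across all V-CST participants and among sub-populations of patients", the sub-populations being race, gender and ethnicity. Neither is divided by sessions, time or number of people. In the same section, enrollment, attendance, attrition and data completeness are all defined as percentages.

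Active AE collection is tied to the sessions:

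- Section 6.2.3: "five process measures will be collected by the V-CST facilitators at each session", and AEs are one of the five.
- Section 7.2: "V-CST facilitators will monitor participants for harm at all times during therapy delivery".
- Section 9.3: "the possibility of AEs will be monitored at every V-CST session".
- The schedule in Section 6.1 marks AEs only in the treatment column.

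There is a second route for some events. The AE definition in Section 7.3 is broad ("Any unfavorable medical occurrence in a clinical research study participant"), and the same section has the referral site report to the coordinating site "In the event of hospitalizations or death of any study participant (intervention or control group) identified by the referral site".

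Exposure can also end because of AEs. Under Section 9.3, involvement in V-CST is "discontinued altogether when instances of such heightened stress are observed in more than two separate V-CST sessions".

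**The concern.** A participant may attend anywhere from 0 to 14 sessions, and stress in a session can be recorded only when the person is there. Two subgroups with the same risk per session will therefore produce different AE totals if they differ in size or attendance, and two subgroups with different risks can produce the same total. Section 10.3.3 examines attendance by race, gender and ethnicity, the same groupings over which AEs are summed, but does not connect the two.

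The totals may be acted on. Under Section 10.3.2 the Quality Control Committee reviews AE and adherence reports every two weeks and may adjust the protocol. Section 9.3 asks the statistician to judge whether events in a V-CST group raise statistical as well as clinical concerns, and names no denominator, although groups hold up to eight people and attendance will vary. When few events are expected, a difference of one or two between unequal groups is easily misread.

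**Working it through.** The documents state no AE rate, attendance rate or subgroup size, so there is no figure of the plan to reproduce. The numbers below are illustrative.

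**Inputs from the documents.** At most 56 people are referred to V-CST and there are 14 sessions (Section 5.1), so at most 56 × 14 = 784 person-sessions. V-CST ends once stress has been seen in more than two sessions (Section 9.3).

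**Assumptions.** 2 AEs per 100 attended sessions in every subgroup; attendance of 50% or 90%; subgroups of 16, 28 and 40.

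**Formulas.** Expected sum = n × 14 × attendance × rate. Mean per participant = 14 × attendance × rate. Exposure-based rate = AEs / sessions attended.

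| n | Attendance | Sessions attended | Expected sum | Mean per participant | AEs per 100 sessions |
|---|---|---|---|---|---|
| 40 | 90% | 504.0 | 10.1 | 0.25 | 2.0 |
| 16 | 90% | 201.6 | 4.0 | 0.25 | 2.0 |
| 28 | 90% | 352.8 | 7.1 | 0.25 | 2.0 |
| 28 | 50% | 196.0 | 3.9 | 0.14 | 2.0 |
| 16 | 50% | 112.0 | 2.2 | 0.14 | 2.0 |

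1. *Size.* At 90% attendance the sum falls from 10.1 to 4.0 between n = 40 and n = 16, while the mean per participant stays at 0.25. Size distorts the sum only.
2. *Attendance.* At n = 28 the sum is 7.1 against 3.9 and the mean 0.25 against 0.14. Both ratios are 0.9 / 0.5 = 1.8.
3. *Masking.* Equal sums of 5 with n = 28 mean 5 / 352.8 = 1.4 per 100 sessions at 90% attendance and 5 / 196 = 2.6 per 100 at 50%, again a 1.8-fold difference.

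**Effect of the discontinuation rule.** This is an exact session-by-session recursion at full attendance, with at most one AE per session, stopping at the third session with an AE.

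| Risk per session | Mean count, no stopping | Mean count, with stopping | Change | Expected sessions | AEs / sessions |
|---|---|---|---|---|---|
| 5% | 0.700 | 0.695 | −0.7% | 13.91 | 5% |
| 10% | 1.40 | 1.34 | −3.9% | 13.45 | 10% |
| 30% | 4.20 | 2.78 | −34% | 9.28 | 30% |
| 50% | 7.00 | 2.99 | −57% | 5.99 | 50% |

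**Limit of the per-session rate.** The last column returns the assumed risk because everyone in a row has the same risk. If half the participants have 5% risk and half 50%, the pooled rate is (0.695 + 2.993) / (13.907 + 5.985) = 3.688 / 19.892 = 0.185, while the average risk over participants is (0.05 + 0.50) / 2 = 0.275. People at high risk contribute fewer sessions, so a person-level summary is needed beside the rate.

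**Limit of the person-level summary.** The chance of at least one AE, 1 − (1 − attendance × rate)^14, also depends on attendance. At 2 per 100 sessions it is 1 − 0.982^14 = 22.5% at 90% attendance and 1 − 0.990^14 = 13.1% at 50%. Neither summary is enough alone.

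**The case against.** The strongest reply is that this is a quality-assurance metric in a minimal-risk pilot. The protocol expects no safety events, no hypothesis or stopping rule uses the sum, and the committee that receives the AE reports, which includes the biostatistician, also receives session-by-session adherence reports. The by-group review in Section 9.3 is triggered by participants being discontinued, not by an AE total. All of this stands and limits the importance of the point. It does not supply the missing denominator.

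Four stronger readings are tempting, and the documents do not support them.

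- *AEs are sought only in attended sessions.* This holds for stress-type events. Hospitalizations and deaths in either arm also arrive through the referral sites (Sections 7.3 and 7.3.1) and do not depend on attendance. A per-session rate suits them badly.
- *The figures reflect attendance and size rather than risk.* At a given size and attendance the counts still rise with risk, so they are confounded, not empty. The per-participant distribution, which the plan also calculates, does not scale with subgroup size, although the plan does not say it will be produced by subgroup.
- *A planned subgroup safety comparison is biased.* Section 10.3.3 gives a comparative purpose for enrollment, attendance and completeness, but for AEs says only that counts are summed. A comparison is what a reader may make of the sums, not a stated analysis.
- *The three-session rule seriously distorts the counts, so that three events in 3 sessions look the same as three over 14.* Under the rule, stress in a third session ends V-CST. The 14-session case arises only if that third session is the last one or the events cluster in at most two sessions. The rule counts sessions, not events, so it does not cap a person's count at three. Its effect is large only at risks such as 30% to 50% per session, far from what the protocol expects.

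**Conclusion.** The point holds for session-observed AEs, mainly stress. As written, the subgroup sums in Section 10.3.3 are confounded with subgroup size and attendance, and the per-participant counts with attendance. At equal risk per session, 90% against 50% attendance produces a 1.8-fold difference. That ratio needs only the two assumed attendance levels and does not depend on the AE rate. Event-driven discontinuation changes the mean count by less than 4% at 10% risk per session or below, and becomes material only if events are frequent.

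The consequence is modest: a safety and quality-assurance summary that is hard to interpret, with no effect on any hypothesis test. It is worth correcting because the necessary data already exist.

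**What to change.** In Section 10.3.3, for AEs observed in sessions, report overall and by race, gender and ethnicity:

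- the number and percentage of V-CST participants with at least one AE;
- AEs per attended session (total events / total sessions attended);
- the number of participants and of sessions attended beside every count.

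Intervals for the rate should allow for repeat events within a person, by a cluster-robust variance or a bootstrap over participants. A simple exact Poisson interval treats repeat events as independent. Report hospitalizations and deaths separately, per participant. Show the same denominators in the by-group review in Section 9.3.

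The cost is a few sentences in 10.3.3 and 9.3. No new data are needed, since attendance at each session is already recorded (Sections 5.1 and 5.4), and no clinical rule changes. There are two drawbacks. Subgroup intervals will be wide: at the assumed 2 per 100, even full attendance by all 56 gives only 784 × 0.02 = 15.7 events. And the pooled per-session rate remains affected by event-driven discontinuation when risk differs between participants, which is why the person-level percentage should stand beside it.

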### **10.3.4 Protocol Deviations**

Following each V-CST session, in standard practice the V-CST facilitators complete a brief protocol adherence checklist indicating which components of the V-CST protocol were completed. Protocol adherence checklists will be reviewed by the Quality Control Committee when meeting every two weeks during the intervention delivery phases of the trial, and more frequently in the case of AEs.

### **10.3.5 Monitoring**

Intervention protocol compliance will be monitored by the Quality Control Committee reviewing protocol adherence checklists when meeting every two weeks during the intervention delivery phases of the trial.

## **11 PARTICIPANT RIGHTS AND CONFIDENTIALITY**

Participant rights will be upheld, and participants will be aware that confidentiality regarding their participation is limited due to V-CST being a group therapy in which other individuals participating are aware of the participation of others based on active visual and audio engagement during the course of therapy.

### **11.1 Institutional Review Board (IRB) Review**

This protocol and any subsequent modifications will be reviewed and approved by Advarra, the IRB responsible for oversight of the study. This study will utilize a single IRB (Advarra), and all local IRB will cede to Advarra through a reliance agreement established prior to study start.

## 11.2 Informed Consent Forms

A request for a waiver of informed consent has been requested and approved for this pilot trial. This waiver is deemed justified for the combination of reasons listed below:

Enrollment into the study is considered at the time of randomization as there is no research consent process for this protocol. Intervention group participants will be asked to provide clinical assent for CST referral. The HCS provider will obtain informed clinical assent using a CST informational sheet derived from the CST site standard of care education materials on CST. Risks and benefits of CST, as well as alternative treatments are described in the clinical assent process per standard of care.

Justification for a waiver of informed consent is based on this study involving no more than minimal risk, the protocol cannot be practicably carried out without the requested waiver, and the waiver will not adversely affect the rights and welfare of subjects. This study qualifies as minimal risk based on CST being a low-risk intervention and is being administered as standard of care. Part of the aims of this protocol is to evaluate the feasibility and acceptability of the referral process to establish CST intervention options for PLWD as standard of care. Because it is during the referral process that consent processes would begin, study subjects cannot be consented as that would change the referral process that will be evaluated, and furthermore, the goals of a pragmatic trial such as this one will pilot requires limiting the interference of research activities on standard clinical practice and relying on more organic observational approaches to data capture as possible.

Additionally, the waiver will not adversely affect the rights and welfare of the subjects as the protocol will ensure that referring physicians obtain clinical assent for referral and participants will be engaged voluntarily. As CST is a very low risk non-pharmacological treatment with well-established benefits not readily available in this population, we do not anticipate participants would object to the aims of this protocol to establish CST treatment options; furthermore, in an initial pilot of V-CST, people with dementia who participated commonly reported positive emotional experiences and boosts to their self-esteem, and commonly described the experience of participating as enjoyable ([name] et al., 2021). We will be collecting identifiable information due to the limited ability of the HCS ability to de-identify and burdensome on the staff to request de-identified data only.

Finally, we will inform patients of their participation in the study and provide results of the data analysis after study completion. After the intervention and follow-up time points are completed, we will distribute a letter directly to the participants from their HCS regarding the trial.

## 11.3 Participant Confidentiality

Because V-CST is a group therapy in which multiple participants (up to eight) have direct visual and audio contact with each other, and with the V-CST facilitators, confidentiality of the intervention group is limited. Furthermore, consistent with standard referral practices, the participating HCSs will provide the community-based service provider with the names and contact information of PLWD when making referrals for V-CST, and the community-based service providers will use protected health information (PHI; e.g., names, phone numbers, email addresses)) when enrolling PLWD in V-CST and over the course of treatment. Additionally, to ensure the trial is pragmatic by limiting data management tasks by the referring HCSs, the research will use PHI to track patients over time and across sites. In alignment with the use of PHI, a full waiver of Health Insurance Portability and Accountability Act (HIPAA) authorization is requested for both the recruitment and overall study tasks. The waiver is justified for the following reasons:

- Use or disclosure involves no more than minimal risk to the privacy of individuals because of the presence of an adequate plan to protect health information identifiers from improper use or

disclosure, specifically, maintaining all PHI in a secure Sharepoint file server that is maintained by UMass information technology (IT) department.

- See section 2.3 for protection procedures against loss of confidentiality and efforts to protect personal health information from improper use or disclosure.
- After data analysis is complete, data set will be scrubbed of all identifiers by the UMass research team. Only aggregated data set
- Research could not practicably be conducted without the waiver or alteration. The research is a pilot pragmatic trial, in which the referral sites will provide data on patients who are randomly allocated to the intervention group (to receive V-CST referral) and the control group (no referral). In order to maintain the pragmatic study design, ensure no bias is introduced, and maintain external validity, the researchers will not be able to obtain consent and inform the potential participants of the study procedures, therefore, we need a waiver for HIPAA authorization.
- Research could not practicably be conducted without access to and use of PHI. The use of the PHI is necessary for intervention screening and enrollment, and for linking patient-level data from across sites and over time. Because contacting PLWD using contact information and communicating with PLWD by name are basic tenets of social interaction in the study context, the research could not practicably be conducted without the waiver. Additionally, potential participants will be screened for eligibility to ensure safety of the referral and maintain the integrity of the research design. Finally, PHI will need to be accessed and used to increase the pragmatism of the trial and minimize changes to SOC practice at referral sites.

The confidentiality of patient information beyond the research team will be maintained by storing study data in a HIPAA compliant platform. No paper records are anticipated, but all paper records will be kept in a locked file cabinet locally at the HCS sites and CaringKind. All computer entry and networking programs will be done using encrypted secure file transfers and storage.

